2 INTRODUCTION

The classification of congenital ichthyosis (CI) is complex because the disorder presents in a multitude of forms and phenotypes. The main features, however, are scaling and often thickening of the skin (Vahlquist 2008). The presentation and severity of symptoms can differ greatly by patient and by the form of ichthyosis, but generally include skin inflammation and fragility, pruritus, fissuring and cracking of thickened skin, anhidrosis, and in some severe cases, an increased susceptibility to infection. Recessive X-linked ichthyosis (RXLI), which occurs at a frequency of about one in 2500 (in males), is clinically characterized by widespread, dark brown, polygonal scales, and generalized dryness (Takeichi 2016). The diagnosis can be confirmed using genetic testing to identify a complete deletion of the gene encoding steroid sulfatase (STS) that is located at the terminus of the X chromosome (Nomura 1995). Autosomal recessive congenital ichthyosis (ARCI), which occurs at a frequency of about one in 100,000 to 300,000, is a member of the non-syndromic autosomal recessive CI group which manifests itself clinically as hyperkeratosis and dry, scaling skin across the entire body (Vahlquist 2014); pathogenesis is related to a severely disturbed barrier function due either abnormal corneocytes or to a defective deposition of stratum corneum lipids and can be caused by truncation or missense mutations in the gene encoding keratinocyte transglutaminase type 1 (TGM1) (Vahlquist 2008, Vahlquist 2014).

Isotretinoin is a “natural” retinoid (13-cis isomer of naturally occurring tretinoin [all-trans-retinoic acid {RA}]) that was initially developed as a synthetic retinoid, but it is also present in cells as a naturally occurring metabolite (Digiovanna 2013). Isotretinoin is structurally and pharmacologically related to vitamin A, which regulates epithelial cell growth and differentiation (GlaxoSmithKline Australia Pty Ltd 2013). Isotretinoin has several pharmacological mechanisms of action that result in the suppression of sebaceous gland activity, reduction of sebum production, reduction of comedogenesis by decreasing hyperkeratinization, suppression of *Propionibacterium acnes* (*P. acnes*), and reduction of inflammation (Layton 2009). Isotretinoin has at least 5 biologically important metabolites: 13-cis-4-oxo-RA (4-oxo-isotretinoin), all-trans-RA (tretinoin), all-trans-4-oxo-RA (4-oxo-tretinoin), 9-cis-RA (alitretinoin), and 9-cis-4-oxo-RA; and can be considered a pro-drug, in which isotretinoin can be metabolized into the naturally occurring tretinoin (or one of the other metabolites) as the active intracellular moiety (Layton 2009). In addition, while some of isotretinoin’s activity may be mediated by tretinoin, the isomerization of isotretinoin (13-cis-RA) into tretinoin (all-trans-RA) does not account for all of the pharmacological effects observed upon use of this retinoid (Blaner 2001). Thus, isotretinoin’s broader range of activity compared to other retinoids makes it advantageous for clinical development.

Oral isotretinoin (Accutane®) capsules were first approved by the United States (US) Food and Drug Administration (FDA) as treatment for severe recalcitrant nodular acne in 1982 (Roche Laboratories Inc 1982). Teratogenicity is regarded as one of the most serious potential adverse effects of oral retinoids, while common mucocutaneous side effects are dose-dependent and can be managed by modification of the dose (e.g., reductions and/or drug holidays) and additional symptomatic therapy (e.g., moisturizers). Topical formulation of isotretinoin, Isotrex®

gel and cream, 0.05%, has since been approved in various countries outside of the US for the treatment of mild to moderate acne vulgaris, characterized by comedones, papules, and pustules ([GlaxoSmithKline Australia Pty Ltd 2013](#), [GlaxoSmithKline UK Limited 2014](#)). Another topical formulation, isotretinoin cream, 0.1%, has also been studied in various indications including ichthyosis and other disorders of keratinization ([Burge 1995](#), [Steijlen 1993](#)) and acne vulgaris ([Chalker 1987](#), [Dominguez 1998](#), [Hughes 1992](#), [Ioannides 2002](#), [Jensen 1991](#)).

2.1 Study Rationale

Systemic retinoids, including isotretinoin, have been used for the investigational treatment of CI and have demonstrated remarkable efficacy in reducing the clinical signs of the disease while dosing of the drug is maintained. Although not FDA approved, topical formulations of isotretinoin (e.g., 0.05% gel and 0.1% cream) have demonstrated some efficacy in reducing the clinical signs associated with ichthyosis and other disorders of keratinization.

Timber Pharmaceuticals, LLC is developing a topical ointment (0.05%) formulation of isotretinoin called TMB-001 (previously PAT-001) (isotretinoin) ointment for the treatment of CI, including RXLI and ARCI subtypes. An initial Phase IIa study in subjects aged ≥ 12 years has shown favorable efficacy after treatment with TMB-001 0.1% ointment. A subsequent Phase IIb study with TMB-001 0.05% and 0.1% ointment demonstrated reduced clinical signs of CI in subjects aged ≥ 9 years, with significant improvement of Visual Index for Ichthyosis Severity (VIIS)-scaling and the Investigator Global Assessment (IGA) scaling/fissuring severity score.

The purpose of this Phase III study is to investigate the efficacy and safety of topically applied TMB-001 0.05% in subjects aged ≥ 6 years with RXLI or ARCI while the Optional Maximal Use arm will evaluate systemic exposure and safety.

2.2 Background

CI is a large, heterogeneous family of inherited skin disorders of cornification resulting from an abnormality of skin keratinization ([Vahlquist 2008](#)).

The management of CI is a life-long endeavor, which remains largely symptomatic (i.e., emollients with or without keratolytics) and commonly focused on reducing scaling and/or skin lubrication with both systemic and topical treatments ([Vahlquist 2008](#)). A first-line therapy includes hydration and lubrication accomplished by creams and ointments containing low concentrations of salt, urea, or glycerol, which increases the water-binding capacity of the horny layer. Addition of keratolytics is used to decrease corneocyte cohesiveness, to promote desquamation, and to dissolve keratins and lipids (e.g., α -hydroxy acids, salicylic acid, high-dose urea, propylene glycol, *N*-acetylcysteine, and retinoids). Systemic retinoid treatment is reserved for those patients who are refractory to topical agents because of long-term adverse effects and teratogenicity ([Digiovanna 2013](#)); however, the investigational use of oral isotretinoin has demonstrated remarkable efficacy when used for the treatment of ichthyoses and is believed to be attributable to isotretinoin's ability to decrease hyperkeratinization ([Vahlquist 2008](#), [Digiovanna 2013](#)). For the treatment of CI, it would be desirable to have a topical formulation of isotretinoin, such as TMB-001, Timber's proprietary isotretinoin ointment, as it would afford

targeted delivery of the drug at the disease tissue site, while potentially minimizing systemic exposure compared to that of systemic retinoid treatment, and additionally providing hydration and lubrication to the diseased skin.

An initial Phase IIa, multicenter study in subjects aged ≥ 12 years showed topically applied TMB-001 ointment (0.1%) to be safe, tolerable, and supporting a favorable efficacy signal with improvement in overall IGA for CI treatment.

In a subsequent parallel, double-blind, vehicle-controlled Phase IIb study in subjects aged ≥ 9 years with confirmed CI, 10%–90% of total body surface area (BSA) affected, subjects were randomized (1:1:1 ratio) to TMB-001 0.05% (n=11), TMB-001 0.1% (n=10) or Vehicle (n=12) twice daily (BID) for 12 weeks. Key efficacy endpoints at 12 weeks were the proportion of subjects with a $\geq 50\%$ reduction compared with Baseline in VIIS-scaling (VIIS-50); and the proportion of subjects with ≥ 2 -grade reduction in IGA-scaling and fissuring severity score vs Baseline. Adverse events (AEs) and local skin reactions (LSRs) were also assessed. The mean age of the subjects was 34.5 years; 55% and 45% of the enrolled subjects had lamellar ichthyosis (LI) and RXLI subtypes of CI, respectively. Overall, 64% and 40% of Intention-to-treat (ITT) subjects treated with TMB-001 0.05% and 0.1%, respectively achieved VIIS-50 compared with 33% treated with vehicle (nominal P=0.17 for TMB-001 0.05% vs vehicle). Median time (ITT) to VIIS-50 achievement was 28.0 days for TMB-001 0.05% and 54.0 days for TMB-001 0.1% compared with 63.5 days for Vehicle (P=0.02 for 0.05%). Improvement of ≥ 2 -grade IGA score was observed in 55% of TMB-001 0.05% and 40% of TMB-001 0.1% compared with 8% for Vehicle (nominal P=0.02 for 0.05%). Most LSRs were mild or moderate in severity and occurred at Weeks 2 and 4. By Week 12, burning/stinging and erythema were reported in 18% and 36% of subjects receiving TMB-001 0.05% and TMB-001 0.1%, respectively. No subjects reported edema and 18% and 30% of subjects reported mild skin erosions for TMB-001 0.05% and 0.1%, respectively. No hospitalizations, serious adverse events (SAEs) or deaths were observed.

2.3 Benefit/Risk Assessment

While no topical isotretinoin formulation is approved for use in treatment of CI (or any indication in the US), topical formulations of isotretinoin (e.g., 0.05% gel and 0.1% cream) have demonstrated some efficacy in reducing the clinical signs associated with ichthyosis and other disorders of keratinization. In one study, topical 13-cis-RA (isotretinoin) cream 0.1% demonstrated a marked reduction in scaling and an improvement in skin smoothness after 4 weeks of treatment in 40% of subjects (2/7 subjects with non-erythrodermic LI, 2/2 subjects with Darier's disease, and 0/1 subjects with autosomal dominant ichthyosis vulgaris). However, this clinical improvement was accompanied by local skin irritation (e.g., itchy erythema) in responders, and dose modifications were often prescribed to mitigate such effects ([Steijlen 1993](#)). Similarly, topical isotretinoin gel, 0.05% (Isotrex®) demonstrated partial resolution or clearance of hyperkeratosis and papules in the treatment area (10 cm² area) after 3 months of treatment (up to BID as tolerated) in 50% (6/12) of subjects with Darier's disease. In addition, systemic retinoids, including isotretinoin, have been used for the investigational treatment of CI and have demonstrated remarkable efficacy in reducing the clinical signs of the disease while dosing of the drug is maintained ([Vahlquist 2008](#), [Digiovanna 2013](#)).

The most notable adverse reactions with oral isotretinoin are: teratogenicity, dry lip, dry skin, back pain, dry eye, arthralgia, epistaxis, headache, nasopharyngitis, chapped lips, dermatitis, renal or hepatotoxicity, musculoskeletal discomfort, and visual acuity reduced.

The following are concerns for women of childbearing potential (WOCBP):

- Severe birth defects can occur during pregnancy while taking oral isotretinoin, with any amount and even if taken for short periods of time;
- Pregnancy must be avoided 1 month before, during, and for 1 month after treatment.

As with any retinoid, the side effects of TMB-001 may include the following LSRs: burning, dryness, edema, erythema, hyperpigmentation, hypopigmentation, photosensitivity, pruritus, scaling/peeling, stinging, and tenderness.

Systemic exposure is expected to be low given the route of topical administration. In minipigs receiving once daily dermal applications of TMB-001 ointment for 90 days at concentrations of 0.025%, 0.1%, and 0.2%, there was little to no systemic absorption of isotretinoin with most values being near or below the limit of quantitation (0.374 ng/mL).

In addition, in a Phase IIa clinical study of subjects with CI involving 12% BSA, where TMB-001 0.1% and 0.2% ointment concentrations were tested, the serum concentrations of isotretinoin and tretinoin were measured for 12 weeks (n=5). Plasma concentrations of isotretinoin and tretinoin indicated that systemic exposure was minimal within the 4 hours following initial application. Trough concentrations measured on Days 8, 29, 57 and 84 approximately 12 hours following the preceding dose indicated that systemic concentrations of isotretinoin and tretinoin were within range of the endogenous levels measured at Baseline prior to the first application.

More detailed information about the known and expected benefits and risks and reasonably expected AEs of TMB-001 ointment may be found in the Investigator's Brochure.

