4.2 Discussion of Study Design

This is a multicenter, randomized, double-blind, vehicle-controlled Phase III study to evaluate the efficacy and safety of TMB-001 0.05% topical ointment in the treatment of CI. Subjects will be selected according to predefined entry criteria. The study treatment duration is 24 weeks and expected to be sufficient to show a treatment effect.

Isotretinoin is an approved active pharmacological ingredient with a long history of safe use in humans. However, isotretinoin is a known teratogen with an extremely high risk for severe birth defects if pregnancy occur while taking oral isotretinoin in any amount, even for a short period of time. Therefore oral, systemic isotretinoin requires an iPLEDGE program ([iPLEDGE 2012](#)), which is a risk management distribution program mandated by the FDA. To minimize pregnancy risks, WOCBP will only be enrolled if they agree to use highly effective methods of contraception consistently and correctly as described in Table 18 and undergo regular pregnancy testing ([Section 8.3.5](#)).

To minimize bias, subjects will be blinded and randomly assigned to treatment with TMB-001 0.05% or Vehicle ([Figure 1](#)), additionally subjects who had previously been treated with TMB-001 will be excluded from this study but can be enrolled in the optional Maximal Use arm (in a subset of preselected centers). The use of a vehicle control group is consistent with FDA's standard for generating valid scientific evidence to definitively support safety and efficacy. The vehicle group accounts for the effects of treatment that do not depend on the test treatment. The study is designed to mitigate safety risks by using an initial 2:1 randomization (active treatment to vehicle), along with frequent clinic visits over the 12-week treatment period. The subsequent 1:1 randomization of eligible TMB-001 0.05% treated subjects to two dosing regimen (QD or BID) allows for assessment of the optimal TMB-001 0.05% maintenance therapy as well as provides additional safety data for 12 weeks. The cross-over of eligible subjects from the vehicle control group will also provide additional safety data.

Overall, the study design is considered to be scientifically robust and clinically relevant for evaluating TMB-001 0.05% treatment for the safe and effective treatment of CI.

The design of the Optional Maximal Use arm is discussed in [Section 9.1.1](#)

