4.4 End of Study Definition

A subject is considered to have completed the study if he/she has completed the last scheduled visit (Visit 6 for subjects who do not qualify for maintenance therapy, Visit 9 for subjects who qualify for maintenance therapy) per the SoA ([Table 1](#)). The end of the study is defined as the date of the last visit of the last subject in the study.

The end of study definition of the Optional Maximal Use arm is described in [Section 9.1.2](#).

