5.1 Inclusion Criteria

Subjects must fulfill all of the following inclusion criteria to be eligible for participation:

1. Subject is male or female, 6 years of age and older at Visit 2 (Baseline).
2. Subject has provided written informed consent/assent. A subject under 18 years of age must provide written informed assent and be accompanied by the parent or legal guardian at the time of consent/assent signing. The parent or legal guardian must provide informed consent for the subject. If a subject becomes 18 years of age during the study, the subject must provide written informed consent at that time to continue study participation.
3. Females must be postmenopausal (defined as amenorrhea greater than 12 consecutive months in women 50 years of age and older), surgically sterile (hysterectomy, bilateral salpingectomy, or bilateral oophorectomy), or use 2 acceptable forms of birth control. WOCBP must have a negative serum pregnancy test at screening and negative urine pregnancy test (UPT) at Visit 2 (Baseline) (UPTs must have a minimum sensitivity to detect 25 mIU beta-human chorionic gonadotropin [β -hCG]/mL). Methods of acceptable contraception are further defined in [Appendix 4](#). Female subjects who become sexually active or begin to have relations with a partner during the study must agree to use 2 forms of birth control for 30 days prior to having relations and to continue such forms of birth control for the duration of the study.
4. Subject has clinical diagnosis of CI based upon phenotype and has a genetic confirmation of either ARCI (including but not exclusively transglutaminase 1-deficient, ALOX-12B) or RXLI (e.g., deletion of steroid sulfatase gene) subtypes of CI. Other genetically confirmed ARCI mutations can potentially be enrolled as long as the phenotype is consistent with ARCI and the other inclusion criteria are met, as determined by the Investigator (see [Appendix 5](#)).
5. The amount of CI affected skin in the Treatment Area at Baseline will be between a minimum of 10% and maximum of 90% of the total BSA (1% BSA is approximately equal to the surface area of the subject's palm and fingers, with the fingers extended yet grouped together, creating a flat oval-like surface area).
 - **For the Optional Maximal Use arm:** The amount of CI affected skin in the Treatment Area at Baseline will be between a minimum of 75% and maximum of 90% of the total BSA.

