5.2 Exclusion Criteria

A subject is ineligible to enter the study if he/she meets 1 or more of the following exclusion criteria:

1. Subject is pregnant, lactating, or is planning to become pregnant during the study.
2. Subject has inflammatory skin diseases that confound the interpretation of results (e.g., atopic dermatitis) unrelated to ichthyosis.
3. Subject has phenotypic clinical presentation and/or genetic abnormality consistent with non-lamellar type or syndromic ichthyoses (including but not exclusively KRT1, KRT10, KRT2, GJB3, GJB4, CDSN)
4. Subject, in the Treatment Areas, has used: (a) any topical prescription or over-the-counter (OTC) therapies (except emollients, keratolytics, and topical steroids – see below), that are intended for, or that in the opinion of the Investigator, may improve CI within 2 weeks of Visit 2 (Baseline), or (b) keratolytics or topical corticosteroids within 5 days prior to Visit 2 (Baseline).
5. Subject, in the Treatment Areas, has used TMB-001 in the past or oral isotretinoin in the past 12 months (**not applicable for Optional Maximal Use arm**).
6. Subject has used any topical products in the Treatment Areas, including bland emollients, on Visit 2 (Baseline).
7. Subject has used ultraviolet (UV) treatment within 4 weeks prior to Visit 2 (Baseline).
8. Subject has undergone systemic therapies using vitamin A supplements or St. John's Wort within 4 weeks prior to Visit 2 (Baseline). *Note: Use of a multivitamin including vitamin A is not exclusionary provided it is taken as directed on the packaging.*

9. Subject is immunosuppressed (e.g., human immunodeficiency virus, systemic malignancy, graft host disease) or receives systemic immunotherapy.
10. Subject is currently taking concomitant immunosuppressive drugs, including systemic corticosteroids, within 2 weeks of Visit 2 (Baseline).
11. Subject has untreated secondary infections; however, subject may become eligible after successful treatment of his/her infection(s) at the Investigator's discretion.
12. Subject is currently enrolled in an investigational drug or device study or has used an investigational drug or investigational device treatment within 30 days or five half-lives prior to Visit 2 (Baseline).
13. Subject has lesions suspicious for skin cancer (if skin cancer is not ruled out by biopsy), a known personal or immediate family history of squamous cell carcinoma of the skin or melanoma or untreated skin cancers within the Treatment Areas.

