8.5 Treatment of Overdose

Overdose in this study can be defined as either oral ingestion of a tube of TMB-001 or applying the TMB-001 ointment more often than the protocol specified regimen of twice daily.

Oral ingestion of an 80-gram tube of TMB-001 ointment 0.05% is calculated to result in less exposure than achieved with the recommended dosage of oral isotretinoin (80 mg/day). Consequently, the theoretical occurrence of symptoms of overdosage (e.g., hypervitaminosis A) is highly unlikely.

If a subject does receive an overdose of TMB-001 ointment, the subject should be counseled about the teratogenicity of isotretinoin and counseled on the prevention of pregnancy. Any WOCBP must be evaluated for pregnancy and must be warned to avoid pregnancy per the contraceptive measures outlined in [Appendix 4](#) for at least 1 month after overdose. Men should use a condom or avoid reproductive sexual activity with a female who is or might become pregnant for at least 1 month after an overdose. Subjects who present with an overdose should not donate blood for at least 1 month.

In the event of an overdose, the Investigator should:

1. Contact the Medical Monitor immediately.
2. Closely monitor the subject for any AEs, SAEs, and laboratory abnormalities for 1 month after the overdose.
3. Obtain a plasma sample for PK analysis if requested by the Medical Monitor (determined on a case-by-case basis).
4. Document the quantity of the excess dose as well as the duration of the overdose in the eCRF.

Decisions regarding dose interruptions or modifications will be made by the Investigator in consultation with the Medical Monitor based on the clinical evaluation of the subject.

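### The protocol states a 1-month pregnancy-avoidance period after treatment, but its operative contraception rules do not carry it through to all women of childbearing potential

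*Protocol*

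**What the plan says.** Section 2.3 of the Protocol lists two concerns for WOCBP. The first is about the oral drug: "Severe birth defects can occur during pregnancy while taking oral isotretinoin". The second gives the period: "Pregnancy must be avoided 1 month before, during, and for 1 month after treatment".

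The operative rules are elsewhere:

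- **Section 4.2:** "To minimize pregnancy risks, WOCBP will only be enrolled if they agree to use highly effective methods of contraception consistently and correctly". No end date follows.
- **Inclusion criterion 3 (section 5.1):** females must be postmenopausal, surgically sterile "or use 2 acceptable forms of birth control". That general requirement has no end date. A later sentence, on females who become sexually active during the study, asks them "to continue such forms of birth control for the duration of the study".
- **Exclusion criterion 1 (section 5.2):** besides pregnant and lactating women, it excludes a woman who is "planning to become pregnant during the study".
- **Appendix 4, main text:** one highly effective method from Table 18, with no end date.
- **Appendix 4, Table 18:** footnote b asks for two methods during treatment and then for the longer of 30 days after the last dose and one complete menstrual cycle, but only where hormonal contraception may interact with study treatment. Abstinence is tied to the whole risk period, with no length given.
- **Section 8.5:** pregnancy is to be avoided "for at least 1 month after overdose".

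**The concern.** Section 4.2 treats isotretinoin as a known teratogen and bases this trial's contraception requirement on that. Section 2.3 then names a period after treatment that the eligibility and contraception rules do not repeat for WOCBP as a group. A site working from criterion 3 and Appendix 4 would find no instruction telling most users of non-hormonal methods how long to continue after the last dose. Exclusion 1, read literally, does not screen out a woman who intends to conceive soon after her last application. At stake is possible conception inside the month that the protocol itself names.

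The overdose rule makes the gap look unintended. Overdose in section 8.5 includes applying the ointment more often than twice daily. A woman who over-applies therefore has a stated month of avoidance, while one who completes up to 24 weeks of planned dosing has none in the operative text.

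**Working it through.** This is a comparison of text, with some simple timing arithmetic.

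**Step 1. Which rules give a post-dose period, and to whom?**

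| Place in Protocol | Applies to | Post-dose period |
|---|---|---|
| 2.3 | WOCBP, listed as a concern beside an oral-drug statement | 1 month |
| 4.2 | WOCBP | none stated |
| Criterion 3, general requirement | Females not postmenopausal or sterile | none stated |
| Criterion 3, later sentence | Females becoming sexually active on study | to the end of the study |
| Exclusion 1 | Women planning pregnancy | during the study only |
| Appendix 4, main text | WOCBP | none stated |
| Table 18, abstinence | Abstinent women | risk period, length undefined |
| Table 18, footnote b | Hormonal methods that may interact | 30 days or one cycle, the longer |
| 8.5 | WOCBP after overdose | 1 month |

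In the available text, marker b sits on the combined hormonal and the implantable progestogen-only entries, and intrauterine devices and tubal occlusion are listed beneath the latter. The table layout may be damaged, so the footnote's exact reach is uncertain. Its condition concerns hormonal contraception in any case. Condoms and a vasectomized partner carry no stated post-dose period.

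**Step 2. How much of the month does the end point in criterion 3 cover?**

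Assumptions: 1 month = 30 days, as in footnote b, and the last dose falls on the day of the last treatment visit. The result applies only to females who become sexually active on study.

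- *Subject-level reading.* Section 4.4 has a subject complete at "Visit 6 for subjects who do not qualify for maintenance therapy, Visit 9 for subjects who qualify for maintenance therapy". Covered: 168 − 168 = 0 days, or 84 − 84 = 0 days. Uncovered: 30 − 0 = 30 days.
- *Counting the 2-week adverse event follow-up.* Covered: 182 − 168 = 14 days (Maximal Use arm: 98 − 84 = 14). Uncovered: 30 − 14 = 16 days. With the ±2-day follow-up window measured from the end of treatment, cover is 12 to 16 days and the shortfall is 30 − 16 = 14 to 30 − 12 = 18 days.
- *Trial-level reading.* Section 4.4 also dates the end of the study by the final visit of the final subject. Cover then depends on when a woman enrolled. It could exceed 30 days for early enrolees, and for the last subject it falls back to one of the two readings above.

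The protocol does not say which reading criterion 3 intends.

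**Step 3. Are the rules consistent on the number of methods?**

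No. Criterion 3 asks for two forms, the Appendix 4 main text for one method, and footnote b for two in its conditional case.

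**The case against.** The strongest reply is a dilemma about section 2.3. If its sentence binds, it is itself protocol text in mandatory wording, and a woman who stops contraception early and is at risk of pregnancy is not following the protocol. If it only carries over the oral precaution, the protocol sets no 1-month standard for this ointment outside footnote b and overdose. The first half stands this far: a reader might infer that the protocol imposes no post-treatment duty at all, or contains no post-dose duration, and neither is correct. The duty is stated but not carried into the rules that sites apply. The second half does not remove the point. Section 4.2 builds this trial's requirement on the oral teratogenicity, and footnote b and section 8.5 each apply about a month to this product.

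Other replies stand in part:

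- **Consent.** Consent pages and the Investigator's Brochure are not available. A reader might infer that participants are not told about the month; the documents cannot show that.
- **Exposed group.** Tubal occlusion and a vasectomized partner do not lapse at the last dose, and abstinence over the risk period could be read with section 2.3. The group is narrower than all WOCBP.
- **Exposure.** Section 2.3 expects low systemic exposure and reports Phase IIa troughs within the endogenous range. Those data are from 5 subjects with 12% of body surface involved. This trial allows up to 90%, and measuring exposure is the primary objective of the Maximal Use arm, so the question is still open.
- **Other safeguards.** Reported pregnancies go to the sponsor within 24 hours, related post-study serious events are reportable, and the treatment-emergent window runs to 30 days. These record events; none tells a woman to continue contraception.
- **Blinding.** A reader might infer that women stopping in the blinded phase can never be told apart by arm. That holds for earlier withdrawals. Under the Visit 6 response rule, leaving with less than a 1-point improvement points to TMB-001, and leaving with 1 point or more points to vehicle.

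**Conclusion.** The point holds as a failure to carry a stated requirement into the operative rules. Criterion 3, exclusion 1, section 4.2 and the main text of Appendix 4 do not extend section 2.3's month to all WOCBP, and the two explicit post-dose periods reach only subsets.

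Its size cannot be given as a count, because neither document states how many WOCBP are enrolled or which methods they use. A reader might take 0 of 30 days as the shortfall for every woman. The documents do not support that: the figure rests on one reading of section 4.4 and concerns only females who become sexually active on study. For WOCBP in general the right description is that no post-dose duration is stated. A reader might also infer that the 2-week safety contact is too short, but closing this gap needs no longer contact. The absolute risk may be small. The case for a change rests on the drug's known teratogenicity and the low cost of the wording.

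**What to change.** 1. In criterion 3 and the Appendix 4 main text, require all WOCBP to continue the required contraception throughout treatment and then for at least 30 days after the last dose or one complete menstrual cycle, whichever takes longer. Footnote b already uses this period.
2. Extend exclusion 1 to women who plan to conceive within that period.
3. Extend Appendix 4 pregnancy reporting, now limited to pregnancies arising while a woman is participating, to the same period.
4. Use one consistent number of methods, resolving criterion 3's two forms against the single method in Appendix 4.
5. Confirm that the consent form says the same.

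The cost is a protocol amendment, consent wording if it differs, and a slightly longer contraception commitment. No visits or tests are added.
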